6.2 FIDELITY

6.2.1 INTERVENTIONIST TRAINING AND TRACKING

The Engage Model is dependent on the Communication Facilitator. Communication Facilitators have standard training at UPMC prior to moving into their positions. The Training Manual for Communication Facilitators has been uploaded separately.

The Fidelity measures in the Table below will be tracked throughout the duration of the study to ensure that Communication Facilitators are able to provide appropriate hearing care and to verify that there are different levels and amounts of care being provided in different facilities.

Timing	Item	Plan for Measurement	Secondary Measurement
Baseline	HHIE (Scale)	% completed	
	Satisfaction with Participation (Scale)	% completed	
	Family - Zarit Burden	% completed	
	Staff - MOAQ	% completed	
	Hearing Test	% completed	
5-month intervals for research measures	HHIE (Scale)	% completed compared to baseline	
	Satisfaction with Participation (Scale)	% completed compared to baseline	
	Family - Zarit Burden	% completed compared to baseline	
	Staff - MOAQ	% completed compared to baseline	
	Hearing Test	% completed on any residents newly enrolled	
During Engage Model Only			
	Hearing Screening	% screened	
	Residents who failed hearing screening offered a hearing test by audiologist	% offered	time from offer to test by audiologist

	Individuals with documented hearing loss provided with a Communication Plan	% Communication Plans completed	
	Action items on Communication Plan Completed	% of action items implemented within 3 months	% residence adherence with plan
	Non-custom amplifiers	# dispensed	% use of non-custom amplifiers for all residents provide with a non-custom amplifier
	Ongoing support of individuals using technology (custom, non-custom, group)	% seen over 1 week period	
	Staff Educational Sessions conducted within a facility	# of sessions	% of staff attending educational session
	Resident educational sessions conducted within a facility	# of sessions	% of residents attending educational sessions
	Presence of CF	% of weeks	
	Presence of Audiologist	% of months	

6.3 MEASURES TO MINIMIZE BIAS: RANDOMIZATION AND BLINDING

The study is randomized at the facility level with pairs of facilities randomized to cross over to the intervention. Pairing is not random, rather pairing will be conducted to have comparable N across pairs.

The Data Entry System (REDCap) and Database will be constructed in a manner that will not allow the DCs to determine what intervention is currently present in the building (Consult Model or Engage Model). The DCs will be blinded in this manner but may be unintentionally unblinded by resident comments when they are interacting. The research team does not anticipate needing to unblind data collectors at any point however if necessary, to unblind will be the decision of the PI in consultation with the leadership team. The research team is not blinded due to the need to work with the Data Coordinating Center to implement the Engage Model across the study.

The University of Pittsburgh Physical Therapy Data Center will serve as the Data Coordinating Center (DCC) under the direction of [name] (**IR-7**). We will use an electronic data capture (EDC) system which will be built around standardized case report forms. The system will have additional applications

including participant tracking, file uploads, and reporting. The electronic data management system will allow the trial to be paperless, as all data will be input directly by the research staff into a secure web-based system. Data will be collected on facilities, staff, residents and family members with linkage through unique, study specific identifiers. For residents, the data collected are minimal: demographics, hearing test results, use of hearing devices, satisfaction with social participation, hearing- specific HRQoL, hospitalizations, and change in status such as moving or death. The data core analysts will be blinded to condition (IR-6).

6.4 STUDY INTERVENTION/EXPERIMENTAL MANIPULATION ADHERENCE

The Fidelity measures outlined in 6.2.1 will confirm that participants are accessing the intervention at the individual level. Participants also are impacted at the Facility level and the DSC will collect monthly data from the facility about the use of group amplification systems.

7 STUDY INTERVENTION/EXPERIMENTAL MANIPULATION DISCONTINUATION AND PARTICIPANT DISCONTINUATION/WITHDRAWAL

7.1 DISCONTINUATION OF STUDY INTERVENTION/EXPERIMENTAL MANIPULATION

The Engage Intervention is both at the Facility and Individual level. It is care that is provided through UPMC Assisted Living and therefore the resident will be exposed whether enrolled in the study (research measures) or not. The most common reason for a resident to discontinue any level of intervention will be that the resident no longer lives in the building. This also would be the reason for a family member to stop participating. The most common reason for staff to stop participating in the intervention would be relocation of his/her job. All data collected to this point will be used in the analysis.

7.2 PARTICIPANT DISCONTINUATION/WITHDRAWAL FROM THE STUDY

Residents

The reason for participant discontinuation or withdrawal from the study will be recorded on the DCDemographicsBaseline1 (Time1, Time 2, Time 3, Time 4, Time 5) Case Report Form (CRF). All new residents entering the facility during the study will be invited to enroll.

Reasons for discontinuation or withdrawal:

Moved to higher level of care

Moved to hospice care

Deceased

Moved to family

[figure not shown]
Family Members

Typically, family members discontinue or withdraw based on the status of the resident.

Staff Members

Staff members withdraw or discontinue if their job placement moves to another location.

The sample CONSORT diagram below illustrates the tracking of enrollment, loss to follow up, and new individuals entering the study (i.e., people who move into the facility during the study). Individuals lost to follow up will be further characterized related to why they were lost to follow up.

7.3 LOST TO FOLLOW-UP

Missing data prevention and analysis plan: To minimize missing data, we will create a tracking system with reminders in the electronic data capture system that will prompt research staff as to which residents are due for follow-up (**MD-1**). If the resident is temporarily unavailable, e.g., hospitalized, visiting family, the research staff member will document the reason for the missing survey and make multiple attempts to follow up with the individual (**IR-7**). We will continue to attempt to collect data throughout the 7-8 week time frame where the Data Collector is in the building every 5-months. We expect to have at least 1 follow-up assessment for at least 85% of the participating residents, based on our pilot data. We will compare baseline characteristics (e.g., age, hearing loss, original responses to surveys of hearing and satisfaction in participation, sex, race, ethnicity, date entered facility) between residents with any missing follow-up to those without to assess potential biases. We will try to obtain reasons for missed assessments so that we can assess the missing data mechanism (**MD-3**). Missed assessments are captured in the REDCap survey when a staff member or resident can tell us why data was not collected (e.g., the resident is out of the facility due to hospitalization or due to family visit, resident does not want to participate on this day, etc.). The linear mixed models proposed for the analyses assume missing data at random (**MD-2**) and perform as well as multiple imputation given the same assumption of the missing data mechanism. We will conduct sensitivity analyses (**MD-4**) assuming non-ignorable missingness with differential imputation of poor scores and pattern mixture models (**MD-2**). We will compare the results from the sensitivity analyses to our primary analyses to assess the robustness of findings.

As a way to explore the issue of attrition and inclusion of residents after baseline, we propose a sensitivity analysis as was done in a similarly designed open cohort stepped wedge trial for depression management in nursing homes (82). We will use two dummy variables for newcomers and non-completers (lost to follow up, died, relocated) and interactions between these variables and the intervention to see if the intervention effect is different for these subgroups of residents.

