Flyers and advertising on the Facility televisions will be used to introduce the study to residents, staff, and families. Residents will be individually introduced to Data Collectors by current facility staff. This method was recommended by our Stakeholder Advisory Panel and was deemed appropriate by the facility leadership with whom we interact on an ongoing basis. In each facility, we will work with directors to provide surveys to staff through the mechanism deemed most appropriate (paper left in an area where staff receive notifications, direct interaction with Data Survey Coordinator, and/or email). This approach was recommended by our Stakeholder Advisory Panel given that staff in different facilities receive information through different mechanisms. We will work with the facility directors to contact family members through this individual to introduce them to the study and to determine if they would like to be contacted via mail or email for survey completion.

In addition, the mechanisms for providing information described above as well as resident/family meetings will be used to introduce the Engage Model (intervention) into the facility. Families also will receive descriptions of the study and later the Engage Model by mail in case they are not in the facilities. The Engage Model is an intervention at the Facility and Individual Level so all residents, staff, and families are exposed whether they have enrolled in the study or not. This care is provided as part of UPMC Senior Living care and is extended to the three non-UPMC facilities. The Consult Model is already present at all facilities at the beginning

of the study. This is an ongoing intervention that was started 5 years ago. At the time of introduction, the same techniques as listed above were used to inform residents, families, and staff about the program. The Consult Model continues to be promoted through flyers and electronic media (TV screens) in facilities. In addition, all new residents are provided about the access to an Audiologist that the Consult Model provides.

d. Resident, Family, and Staff Retention

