***Census as of 05/01/2021. Census shifts as people leave and enter the facilities.**

g. Estimated yield/consent

Residents:

Our pilot data suggest that we should expect that 85% of residents will agree to or be available to participate in the study measures (Pure Tone Hearing Survey, Hearing Specific Health Related Quality of Life Questionnaire and Satisfaction with Participation Questionnaire). After starting baseline data collection, it became evident that both the Census and the rate of decline has changed from when we completed the pilot study. We adjusted the study to accommodate these changes by adding two locations and adding a data collection time point. Census across the 10 facilities suggests that there are 452 residents and we have planned the study around collecting data from 304.

Families:

Our pilot data suggest that we should expect 58% of family members (compared to enrolled residents) to participate in the survey that will be sent to them.

Staff:

Our pilot data suggest that we should expect 90% of the staff in each facility to participate in the survey that will be sent to them.

h. Estimated lost to follow-up/attrition

Residents:

The updated 60% yield accounts for individuals who decline to participate and individuals who may move or otherwise no longer be in one of the facilities. In our pilot work, no residents dropped out of the study unless they were no longer in the facility. Individuals will move into the facilities over the three years and the study design accounts for including these individuals regardless of the timing of their entry into the study.

Family Members: In our pilot study 58% of families participated and 0 dropped out (this was 58% of the resident enrollment). With this study extending over 3 years there will be families who no longer have a family member in a facility who will stop participating. New families will be included as new residents move into the facilities.

Staff Members: In our pilot study, 2% of staff dropped out over time because they changed positions and moved to different facilities. We will collect surveys on any new staff who join the facility over the time period of the study.

i. Gender and Race

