9.4.7 SUB-GROUP ANALYSES

In an effort to ascertain whether the intervention is more or less effective for certain resident subgroups (**RQ-4, HT-1**), we will explore the following groups (**HT-2**):

(a) those who have different degrees of hearing loss at baseline (~84% expected to have some level of hearing loss) and those who do not;

H_1 The intervention provided by the Engage Model and measured by the HHIE and Satisfaction with Participation will have more impact on residents with hearing loss at baseline as compared to residents with no measured hearing loss.

H_0 The intervention provided by the Engage Model and measured by the HHIE and Satisfaction with Participation will not have a different impact on residents with hearing loss at baseline as compared to residents with no measured hearing loss.

(b) those who have different degrees of hearing loss and use a device (~18-32% of 84%; note these are estimates and the actual percent of device use will be used) compared to those who do not use a device but have different degrees of hearing loss;

H_1 The intervention provided by the Engage Model and measured by the HHIE and Satisfaction with Participation will have more impact on residents with hearing loss who do not use a hearing device at baseline as compared to residents with hearing loss who do use a hearing device.

H_0 The intervention provided by the Engage Model and measured by the HHIE and Satisfaction with Participation will not have a different impact on residents with hearing loss who do not use a hearing device at baseline compared to residents with hearing loss who do use a hearing device.

(c) those with high social participation at baseline (~50%) and those with lower social participation;

H_1 The intervention provided by the Engage Model and measured by Social Participation will have more impact for residents with low social participation at baseline compared to residents with normal or high social participation.

H_0 The intervention provided by the Engage Model and measured by Social Participation will not have a different impact for residents with low social participation at baseline compared to residents with normal or high social participation.

(d) those with high hearing-specific HRQoL (~50%) and those with lower hearing-specific HRQoL. Scores of 0-8 on the HHIE are “low” and 10-40 are “high” with 10% indicating a significant change.⁸³

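### The newcomer sensitivity analysis pools residents who joined under Consult with those who joined after their facility's crossover, so an enrolment difference can look like a difference in effect

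*Combined protocol and SAP*

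**What the plan says.** Section 7.3 introduces the analysis thus: "As a way to explore the issue of attrition and inclusion of residents after baseline, we propose a sensitivity analysis". The method follows: "We will use two dummy variables for newcomers and non-completers (lost to follow up, died, relocated) and interactions between these variables and the intervention", with the stated purpose "to see if the intervention effect is different for these subgroups of residents". The only reference point given for entry is the study baseline. The facility's own crossover is not mentioned.

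Entry is open throughout. Section 7.2 says "All new residents entering the facility during the study will be invited to enroll", and section 5.5(h) says "the study design accounts for including these individuals regardless of the timing of their entry into the study". Under section 5.5(c), "resident/family meetings will be used to introduce the Engage Model (intervention) into the facility".

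The primary model in 9.4.2 has fixed effects for intervention and categorical time, random effects for facility, facility × time and resident, and no covariates. It therefore has no term for when a resident joined. In 9.4.7, subgroup (b) contrasts device users with "residents with hearing loss who do not use a hearing device at baseline"; subgroups (c) and (d) use baseline social participation and baseline HHIE score.

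**The concern.** Two kinds of resident are newcomers. One joins a facility still under Consult, is measured there, and may later cross over, as the baseline cohort does. The other joins after the facility has crossed over and is never observed under Consult. One indicator treats them alike. Newcomers' Consult scores then come only from the first kind, and most of their Engage scores come from the second. If the second kind differ at enrolment, the newcomer × intervention term picks up part of that difference, and 7.3 says the term will be read as a different intervention effect. No analysis in the visible text is limited to residents enrolled before crossover, which would show directly whether late entry matters.

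The same gap reaches the subgroups. A post-crossover entrant has no study assessment before Engage began in the facility. Engage dispenses amplifiers (2.1, 6.1.1). In the pilot work of 4.3, under 5% of residents used personal amplification, yet 63% of those with measured loss accepted a non-custom amplifier. For these entrants, device use at first assessment can already be a result of Engage, and so can the scores that define (c) and (d).

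**Working it through.** **Inputs.** From 9.2: 10 facilities, 5 steps of 2 facilities, 30 residents per facility, effect 0.3 SD, intracluster correlation ρ = 0.20, cluster autocorrelation π = 0.9, individual autocorrelation τ = 0.5, and 7.5% churn per period (stated there for the 8-facility simulations). From 4.1: six measurement times. Assumed: each leaver is replaced one for one; churn of 5%, 15% and 25% as a range; and a shift g = 0.3 SD in post-crossover entrants. The documents give no value for g.

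**Variance model (9.4.2), total variance 1.**
- Facility: ρπ = 0.20 × 0.9 = 0.18
- Facility × time: ρ(1 − π) = 0.02
- Resident: (1 − ρ)τ = 0.80 × 0.5 = 0.40
- Residual: (1 − ρ)(1 − τ) = 0.40

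**The plan's own power first.** For the 8-facility design with 65 residents each, generalised least squares gives SE 0.0925. A t-test at two-sided α = 0.025 with 28 Satterthwaite degrees of freedom gives 80.3% power, against the stated 80%. For 10 facilities of 30 at 7.5% churn it gives 88.6%, or 87.5% with facility sizes scaled to the census. The stated figure is 85%, with α not restated. The model is close enough for the present purpose.

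**Share of newcomers who join after crossover.** Pair k crosses at Time k, and entry can occur at Times 1 to 5.
- Entry cells before own crossover: 0 + 1 + 2 + 3 + 4 = 10
- Entry cells at or after own crossover: 5 + 4 + 3 + 2 + 1 = 15
- Post-crossover share with equal inflow: 15/25 = 60%, from 5/5 in the first pair to 1/5 in the last

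In simulated cohorts at 7.5% churn there are about 44 Consult-era and 70 post-crossover newcomers. They supply about 75 and 153 Engage observations respectively.

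**What the planned model returns.** Truth: effect 0.300 for everyone, interaction 0. Only post-crossover entrants are shifted, by 0.3 SD. Where two figures are shown, they come from separate sets of simulated cohorts.

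| Churn per period | Newcomer × intervention (SE) | Primary estimate |
|---|---|---|
| 5% | +0.077 (0.134) | 0.304 |
| 7.5% | +0.080 (0.113) | 0.306–0.307 |
| 15% | +0.093 (0.093) | 0.316 |
| 25% | +0.113 to +0.117 (0.09) | 0.332–0.333 |

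At 7.5% the false interaction is 0.080/0.3 = 27% of the assumed shift. With g = 0, or with both kinds of newcomer shifted by 0.3 SD, it is exactly 0.

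**What the alternatives return.**
- Indicator for Consult-era newcomers with its intervention interaction, plus a main effect for post-crossover entry: effect 0.300, interaction 0.000. This also holds when both kinds are shifted.
- 9.4.2 model restricted to residents enrolled before crossover: 0.300 when only post-crossover entrants are shifted. The SE rises from 0.0845 to 0.0853 at 7.5% churn (0.0853/0.0845 = 1.009), and by about 4–5% at 25%.
- Post-crossover entry added alone, without a term for Consult-era newcomers: 0.294 if both kinds are shifted. Both terms are therefore needed.
- Post-crossover entry × intervention: not estimable. Those residents are always under Engage, so the product equals the indicator itself.

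**The case against.** Several counter-arguments stand.

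- **The coding is inferred.** Section 7.3 never defines newcomer. Section 9.4.1 cites a separate full SAP dated October 6, 2021, whose text was not available here and which might define it.
- **The selection mechanism is weakly documented.** A reader might infer that publicity for Engage draws different people into the study. Section 5.5(c) says Consult is promoted by flyers and television too, and that new residents are told of it. Engage reaches residents whether or not they enrol (5, 7.1). Enrolling brings only a hearing survey and two questionnaires, with no results shared (8.1). Wanting Engage is therefore no clear reason to enrol. On the other side, 5.5(d) schedules Engage information sessions just before each group enrols and expects facilitator support to keep residents engaged. The target is 60% of census, which leaves room for selection. Neither passage gives a size.
- **At planned churn the false interaction is smaller than its SE**, and it depends wholly on an era-specific difference.
- **Section 7.3 is not the only place that touches entry timing.** Section 9.4.9 offers exploratory terms for periods in the intervention, at facility and resident level, and for periods in the study. These bear on timing but do not separate entry before from entry after crossover.

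These points limit the size and certainty of the concern. They do not show that the pooled term can distinguish selective enrolment from a different effect.

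**Conclusion.** The point holds for the robustness and subgroup analyses. As visible, the newcomer term mixes two kinds of entrant, about 40% and 60% under equal inflow, and part of any difference specific to post-crossover entrants would be read as effect modification. Under the assumed 0.3 SD shift that is about +0.08 SD (SE 0.11) at 7.5% churn and 0.11 to 0.12 (SE 0.09) at 25%. These figures rest on the assumed shift, one-for-one replacement and the correlations in 9.2.

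A reader might go further and infer that the primary result is biased by about 0.05 SD, one sixth of the design effect. Post-crossover entrants supply about 16% of Engage observations and none under Consult, and 0.162 × 0.3 = 0.05. That is a shift in a crude mean. Under the model planned in 9.4.2 the estimate moves by about 0.006 SD at 7.5% churn (0.006/0.0845, or 7% of its SE) and 0.03 at 25%. The documents do not support a serious threat to the primary result at planned churn.

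The subgroup issue does not depend on selective enrolment. For post-crossover entrants, the characteristics that define (b), (c) and (d) are first recorded after Engage has begun. How many classifications this changes cannot be computed from the documents.

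**What to change.** 1. In 7.3, define newcomer. Flag each later entrant as enrolled before or after the facility's own crossover, using enrolment and crossover dates together with the facility entry date listed in 8.1.
2. Keep the newcomer × intervention term only for those who joined under Consult, with their own main effect. Enter post-crossover entry as a main effect only, and state that its interaction with intervention cannot be estimated. The first pair to cross has no Consult-era newcomers, so this interaction rests on the other four pairs.
3. Prespecify as a sensitivity analysis the 9.4.2 model restricted to residents enrolled before their facility's crossover.
4. For subgroups (b), (c) and (d), classify residents only from an assessment made before their facility's crossover. Report post-crossover entrants separately.

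Cost: plan wording and a few refits on data already held. The primary analysis is unchanged. The restricted analysis has an SE about 1% wider at 7.5% churn and about 4–5% wider at 25%. Post-crossover entrants leave the three subgroup analyses, which lose some precision. If the separate SAP already makes this split, a cross-reference in 7.3 and 9.4.7 is enough.
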